8.5.1. Laboratory Values Meeting Hy’s Law Criteria

All occurrences of possible drug-induced liver injury that meet Hy's law criteria, defined as all of the below, must be reported by the investigator to the sponsor as a serious adverse event:

- ALT or AST increase of >3× the ULN
- total bilirubin increase of >2× the ULN
- absence of initial findings of cholestasis (ie, no substantial increase of alkaline phosphatase)

An adverse event that does not meet any of the criteria for seriousness listed above will be regarded as a non-serious adverse event.

The serious adverse events will be summarized as indicated in Section 8.3.

8.5.2. Other Clinical Laboratory Tests

At the screening visit, patients will be tested for human immunodeficiency virus (HIV), hepatitis B surface antigen (HBsAg), hepatitis C antibody, and thyroid stimulating hormone. Data will be listed.

Beta-human chorionic gonadotropin tests in serum will be performed for all women of childbearing potential at the screening visit. Data will be listed.

Follicle-stimulating hormone (FSH) test (for postmenopausal women only) will be performed at screening and baseline visit for data collected up to and including Study TV48125-PN-20028 protocol amendment 04, but at screening only for data collected following Study TV48125-PN-20028 protocol amendment 05 The data will be summarized using descriptive statistics.

A urine drug screen will be performed at the time points specified in Table 1 in the study protocol. Data will be listed.

8.6. Physical Examinations

Physical examinations, including height (to be measured at the screening visit only) and weight, will be performed at the time points specified in Table 1 in the study protocol. Any physical examination finding that is judged by the investigator as a clinically significant change (worsening) compared with a baseline value will be considered an adverse event, recorded on the eCRF, and monitored as described in the study protocol.

Descriptive statistics for weight and height will be provided. Abnormal physical examination findings will be summarized by visits.

8.7. Vital Signs

Vital signs (blood pressure [systolic/diastolic], respiratory rate, oral body temperature, and pulse) will be measured at the time points detailed in Table 1 in the study protocol.

Summary statistics for vital signs (blood pressure [systolic/diastolic], respiratory rate, oral body temperature, and pulse) will be presented at baseline, week 4, week 8, week 12, week 16 (end of treatment), week 30 (end of study), and last assessment. Vital signs values and changes from baseline to each visit will be summarized using descriptive statistics.

Summaries of potentially clinically significant abnormal values will include all postbaseline values (including scheduled, unscheduled, and withdrawal visits). The incidence of potentially clinically significant abnormal values will be summarized using descriptive statistics with the criteria specified in Table 5. Systolic and diastolic blood pressure will be included in all summaries.

Table 5 specifies the criteria for identifying vital signs as potentially clinically significant abnormal values. Note that in order to qualify as potentially clinically significant abnormal, a value needs to meet both criteria below: ie, have a value beyond the criterion value and a change of at least the magnitude specified in the change relative to baseline column.

Table 5: Criteria for Potentially Clinically Significant Vital Signs

Vital Sign	Criterion value	Change relative to baseline
Pulse	≥120 bpm	Increase of ≥15
	≤50 bpm	Decrease of ≥15
Systolic blood pressure	≥180 mm Hg	Increase of ≥20
	≤90 mm Hg	Decrease of ≥20
Diastolic blood pressure	≥105 mm Hg	Increase of ≥15
	≤50 mm Hg	Decrease of ≥15
Respiratory rate	<10 breaths/min	
Body temperature	≥38.3°C	Change of ≥1.1°C

bpm=beats per minute

Listings for potentially clinically significant abnormal laboratory data will be presented.

8.8. Electrocardiography

A 12-lead ECG will be recorded at the time points detailed in Table 1 of the study protocol.

All ECG results outside of the reference ranges will be judged by the investigator as belonging to one of the following categories:

- abnormal and not clinically significant
- abnormal and clinically significant

Any ECG finding that is judged by the investigator as clinically significant (except at the screening visit) will be considered an adverse event and recorded on the source documentation and in the eCRF.

Shifts (normal and abnormal) from baseline to overall result interpretation, week 12, week 16 (end of treatment), and last assessment will be summarized using patient counts. For overall result interpretation the worst postbaseline finding for the patient (the abnormal finding if there are both normal and abnormal findings) will be used in the summaries. Summary statistics for ECG variables will be presented. Actual values and changes from baseline to week 12, week 16 (end of treatment), and last assessment will be summarized using descriptive statistics.

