
A secondary objective of the study is to evaluate the safety and tolerability of fremanezumab administered subcutaneously in adult patients with FM.
	
The safety and tolerability endpoints are as follows:
 
 • occurrence of adverse events • change from randomization to week 12 in the clinical laboratory tests (serum chemistry, hematology, and urinalysis) • change from baseline to week 12 in vital signs (pulse, respiratory rate, systolic and diastolic blood pressure, and oral body temperature measurements at each visit) • clinically significant changes in physical examination, including body weight • abnormal standard 12-lead electrocardiogram (ECG) findings • tolerability at the injection site including but not limited to pain, erythema, induration, and ecchymosis • occurrence of hypersensitivity/anaphylaxis reactions using standardized criteria (Appendix C of the study protocol) • suicidal ideation and behavior as measured by the Columbia-Suicide Severity Rating Scale (C-SSRS) • number (%) of patients who did not complete the treatment (Kaplan-Meier Survival Analysis) due to adverse events

1.2. [REDACTED]
[REDACTED]

		
 • [REDACTED] • [REDACTED]
		
 • [REDACTED] • [REDACTED] • [REDACTED] • [REDACTED] • [REDACTED] • [REDACTED] • [REDACTED]

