4.2. Specification of Baseline Values

The baseline values are defined as the last non-missing assessments before the first dose of IMP unless otherwise specified.

Baseline value for the average of the daily average PI-NRS pain score is defined as the average of the daily average PI-NRS score over the last 14 days before the first dose of IMP drug (day -14 to day -1) and will be calculated using formula [1].

Baseline value for the average of the daily worst PI-NRS pain score is defined as the average of the daily worst PI-NRS score over the last 14 days before the first dose of IMP (day -14 to day -1) and will be calculated using formula [1].

The baseline values for the following variables are measured on the day of the first study drug (day 1) before the first dose of study drug.

- individual components of the FIQR: symptom subscore, impact subscore, and functional subscore score
- PROMIS Physical Function SF12a score
- PROMIS Fatigue SF8a score
- HADS score
- EQ-5D-5L
- POMS-2A Short Form score

The baseline value for IMD assessment rating is measured at the screening visit.

PROMIS Sleep Disturbance SF 8a score are collected on e-diary weekly during BAPS. The baseline PROMIS Sleep Disturbance SF 8a scores will be the mean of the weekly scores recorded during last 14 days before the first dose of IMP drug (day -14 to day -1).

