8.3. Adverse Events

An adverse event (AE) is any untoward medical occurrence in a patient administered a pharmaceutical product which does not necessarily have to have a causal relationship with this treatment.

For recording of AE, the study period is defined for each patient as the time period from signature of the informed consent form (ICF) to the end of the follow-up period or the early termination visit for patients who discontinued from the study for any reason. Any AE occurring on or after the first dose of study drug is considered a treatment-emergent AE (TEAE). All AE summaries will be conducted for TEAEs.

The following are considered protocol-defined adverse events of special interest (AESI) to be sent to the sponsor's Global Patient Safety and Pharmacovigilance (GPSP) Department for evaluation:

- ophthalmic-related adverse events of at least moderate severity, as determined by the investigator
- severe hypersensitivity reactions

All AEs will be coded using MedDRA. The incidence of AEs will be summarized using descriptive statistics by SOC and preferred term (PT). Each patient will be counted only once in each PT or SOC category for the analyses of safety.

Statistical Analysis Plan

Summaries will be presented for all AEs (overall and by severity), AEs determined by the investigator to be related to test IMP (ie, reasonable possibility) (defined as related or with missing relationship) (overall, overall by severity, serious AEs, and AESI), serious AEs, AESI, AEs causing discontinuation from treatment, AEs causing early termination from the study, injection site AEs, and AEs leading to death.

Listings of AEs, AESI, serious AEs, injection site AEs, and AEs leading to early termination will be presented separately.

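### The ECG shift table uses two levels (normal, abnormal) although each abnormal ECG is graded for clinical significance, so worsening within the abnormal category does not show as a shift

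*SAP*

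**What the plan says.** SAP 8.8 (and protocol 7.7 in the same terms) grades abnormal ECGs: "All ECG results outside of the reference ranges will be judged by the investigator as belonging to one of the following categories". The two categories are abnormal but NCS, and abnormal and CS. With normal, that makes three possible states for each ECG.

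The table planned in the same SAP section has two: "Shifts (normal and abnormal) from baseline to overall result interpretation, week 12, week 16 (end of treatment), and last assessment", shown as patient counts. For the overall interpretation the rule is that "the worst postbaseline finding for the patient (the abnormal finding if there are both normal and abnormal findings) will be used in the summaries". It does not say how to choose between an NCS and a CS abnormality.

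Three other provisions bear on the point:

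- SAP 8.8: "Any ECG finding that is judged by the investigator as clinically significant (except at the screening visit) will be considered an adverse event". SAP 8.3 adds: "All AE summaries will be conducted for TEAEs".
- SAP 8.8 also plans descriptive statistics for the ECG variables, as actual values and changes from baseline at week 12, week 16 and last assessment.
- SAP 4.2: "The baseline values are defined as the last non-missing assessments before the first dose of IMP unless otherwise specified". An NCS abnormal ECG can therefore be a patient's baseline.

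The endpoint in SAP 1.1 is worded as "abnormal standard 12-lead electrocardiogram (ECG) findings", with no split by clinical significance.

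**The concern.** The point of a shift table is to set each patient's postbaseline state against that patient's own starting state. Here the plan requires a grade of clinical relevance and then collapses it in the one ECG table that compares interpretation with baseline. SAP Tables 4 and 5 set thresholds of potential clinical significance for laboratory tests and vital signs, and there is no such table for ECG. The investigator's grade is thus the only marker of clinical relevance in the ECG section, and no ECG table uses it.

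The patients concerned can be in the trial. Exclusion criterion f (protocol 4.2) turns on clinically significant or unstable disease, with the ECG as one source of evidence. It does not exclude every abnormal tracing.

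Abnormal ECG findings are a stated safety endpoint, and protocol Table 1 schedules on-treatment ECGs only at Visits 6 and 7. At stake is whether a reader can see, by arm, how many patients moved to a clinically significant ECG and from what starting point.

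**Working it through.** The documents state no figure to reproduce. The check lists every transition between the three states and places each in the planned two-level table.

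**Inputs.** States: normal, NCS, CS (SAP 8.8, protocol 7.7). Table categories: normal, abnormal (SAP 8.8). Worst-finding rule: abnormal over normal (SAP 8.8). The parenthesis after the word shifts can be read as the list of table categories, because the laboratory shifts in SAP 8.5 use the same form with three levels.

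| Baseline | Postbaseline | Direction | Cell in the planned table |
|---|---|---|---|
| normal | normal | unchanged | normal to normal |
| normal | NCS | worse | normal to abnormal |
| normal | CS | worse | normal to abnormal |
| NCS | normal | better | abnormal to normal |
| NCS | NCS | unchanged | abnormal to abnormal |
| NCS | CS | worse | abnormal to abnormal |
| CS | normal | better | abnormal to normal |
| CS | NCS | better | abnormal to abnormal |
| CS | CS | unchanged | abnormal to abnormal |

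**Result.** 3 × 3 = 9 transitions collapse to 2 × 2 = 4 cells, holding 1 + 2 + 2 + 4 = 9 transitions.

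- The abnormal-to-abnormal cell pools four: two unchanged, one worse, one better.
- The normal-to-abnormal cell pools two worsening transitions of different clinical weight.
- Of the three worsening transitions, two appear as a shift, not separated from each other, and one (NCS to CS) appears as no shift.

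This holds at week 12, week 16, last assessment and for the overall interpretation. A patient with an NCS ECG at week 12 and a CS ECG at week 16 is simply abnormal overall, because the rule does not order the two.

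**Size.** The number of patients hidden in an arm is n × p × q, where p is the proportion with an NCS ECG at baseline and q is the proportion of those who then have a CS finding. The documents give neither p nor q, so the product cannot be computed.

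**The case against.** The strongest reply is that the important information is reported elsewhere. A CS finding after the first dose is an adverse event, is counted once per patient in its system organ class and preferred term, is tabulated by severity, relation and seriousness, and is listed. Changes in ECG variables are summarized whatever the baseline category. The two-level table also reports the endpoint as worded. All of that stands, and it limits the point to loss of detail. It does not close the gap, because the adverse event tables show neither baseline ECG status nor how many patients had an ECG, and the continuous summaries do not carry the investigator's interpretation.

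A reader might infer more in four ways, none of which the documents support:

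- **That clinically significant ECG worsening goes unreported.** It does not, given the adverse event route.
- **That the SAP contradicts the protocol.** The endpoint has no CS/NCS split, and protocol 9.8.2 asks only for descriptive summaries of ECG changes.
- **That a number of patients per arm is misclassified.** Assuming 10% to 40% NCS at baseline and the planned 80 per arm gives 8 to 32 patients (0.10 × 80 and 0.40 × 80). That rate is only an assumption, and the result counts patients who could be masked, not patients who are. Nor is 80 the likely final arm size: the study stopped for futility, and 153 had been randomized at Amendment 05 (about 51 per arm). For the same reason, nothing shows that non-significant changes dominate the table.
- **That a cardiovascular signal is being hidden.** Protocol 1.3.1 calls the risk theoretical and reports no relevant cardiovascular events in completed studies.

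A practical objection also stands in part. Protocol 7.7 has a physician at a central facility interpret the ECG while the investigator assigns the grade. Only CS findings are expressly sent to the eCRF, so it is not established that the NCS grade is a database field.

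**Conclusion.** The point holds as a modest weakness in a descriptive safety table. The planned shifts cannot show NCS-to-CS worsening, cannot separate normal to NCS from normal to CS, and rest on a worst-finding rule that does not rank the two abnormal grades. This follows from the wording of SAP 8.8 alone and needs no assumed rate. It affects no inferential analysis, and post-dose CS findings remain visible as adverse events. How many patients it touches is unknown. It is worth correcting because the change is small and no other planned summary shows worsening in ECG interpretation against baseline status.

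**What to change.** In SAP 8.8:

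- Use three shift levels: normal; abnormal, NCS; abnormal, CS. Apply them to week 12, week 16, last assessment and the overall worst postbaseline finding.
- Define worst by that order, with CS the worst.
- Add the number of patients per arm with a new CS finding, meaning CS after baseline in a patient whose baseline was normal or NCS, alongside the number with a baseline and at least one postbaseline ECG.
- State whether the investigator's grade or the central reading described in protocol 7.7 feeds the table.

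The cost is SAP wording, one more row and column in an existing table, some sparse cells, and a check that the NCS grade is held in the database. If it is not, the source must be settled before the table is programmed. SAP 2.5.2 has SAP amendments approved before database lock, and the change should be made then.

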8.9. Concomitant Medications or Therapies

Concomitant therapies and medications, including medications that are taken on an as needed basis and occasional therapies, will be monitored during the study. Details of prohibited medications may be found in the study protocol. All concomitant medications will be coded using the WHO Drug Dictionary.

The incidence of concomitant therapies and medications will be summarized using descriptive statistics by therapeutic class category and preferred term. Patients are counted only once in each therapeutic class, and only once in each preferred term category. Concomitant therapies and medications will include all medications taken after the 1st dose of study drug administration up to the end of study as defined in the study protocol.

Similarly the prohibited medications will be summarized separately.

8.10. Columbia-Suicide Severity Rating Scale

The C-SSRS will be used to assess the patient's suicidal ideation (severity and intensity) and behavior. The C-SSRS Baseline/Screening version will be administered by certified site staff at Visit 1, and the C-SSRS Since Last Visit version will be completed by certified site staff at all other time points, as described in Table 1 of the study protocol. Any significant findings on the C-SSRS require evaluation by the site investigator.

Patients having positive findings will be listed.

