- f. known history of clinically significant or unstable hematological, cardiac, or thromboembolic events (ie, arterial or venous thrombotic or embolic events, including cerebrovascular accident [including transient ischemic attacks], deep vein thrombosis, or pulmonary embolism); renal, endocrine, pulmonary, gastrointestinal, genitourinary, or neurologic disorders [exclusive of FM]; infectious, hepatic, or ocular disease, at the discretion of the investigator, as determined by a medical and psychiatric history; and physical examination, 12-lead ECG, serum chemistry, hematology, coagulation, and urinalysis). Abnormal test results may be repeated for confirmation.
- g. moderate or severe major depressive symptoms as assessed by the HADS Depression Subscore >14 (at the Screening Visit and/or the BAPS Visit)
- h. known history of suicide attempt, suicidal behavior, or suicidal ideation within the last 12 months (a response of “yes” to questions 4 or 5 on the suicidal ideation portion of the C-SSRS), or have been assessed as a significant risk to commit suicide at the Screening Visit or Randomization Visit
- i. lifetime history of any psychotic and/or bipolar disorder as assessed by the MINI
- j. current, untreated, moderate or severe major depressive disorder and/or anxiety disorder as assessed by the MINI. Patients with currently treated major depressive disorder and/or anxiety disorder can be included, provided that according to the investigator’s judgment, there have been no clinically significant changes in symptoms while on a stable dose of allowed antidepressants or antianxiety medications for at least 90 days prior to screening, and that the dosage of antidepressant or antianxiety medication will be maintained for the duration of the study.
- k. current eating disorders as assessed by the MINI
- l. known infection or history of human immunodeficiency virus, tuberculosis, or chronic hepatitis B or C infection, or are antigen positive for hepatitis B at screening
- m. past or current history of cancer in the past 5 years, except for appropriately treated non-melanoma skin carcinoma (basal carcinoma)
- n. known history of hypersensitivity reactions to injected proteins, including mAbs and animal venoms, or a history of Stevens-Johnson Syndrome/toxic epidermal necrolysis syndrome
- o. known history of hypersensitivity or intolerance to the use of acetaminophen
- p. known hypersensitivity or intolerance to the components in the formulation of fremanezumab

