9.8.2. Safety Analysis

All adverse events will be coded using the Medical Dictionary for Regulatory Activities. Each patient will be counted only once in each preferred term or system organ class category for the analyses of safety. Summaries will be presented for all adverse events (overall and by severity), adverse events determined by the investigator to be related to test IMP (ie, reasonable possibility) (defined as related or with missing relationship) (overall and by severity), serious adverse events, and adverse events causing early termination from the study. Summaries will be presented by treatment group and for all patients. Patient listings of serious adverse events and adverse events leading to early termination will be presented.

The number and percentage of patients who did not complete the treatment due to lack of efficacy or adverse event will be summarized using descriptive statistics, and the time to treatment discontinuation due to lack of efficacy or adverse event will be analyzed using the Kaplan-Meier Survival Analysis method.

Changes in laboratory, ECG, vital signs measurements, and C-SSRS data will be summarized descriptively. All values will be compared with predefined criteria to identify potentially clinically significant values or changes, and such values will be listed.

The use of concomitant medications will be summarized by therapeutic class using descriptive statistics.

For continuous variables, descriptive statistics (n, mean, standard deviation, median, minimum, and maximum) will be provided for actual values and changes from baseline to each time point. For categorical variables, patient counts and percentages will be provided. Descriptive summaries of serious adverse events, patient early terminations due to adverse events, and potentially clinically significant abnormal values (clinical laboratory or vital signs) based on predefined criteria will be provided as well.

If any patient dies during the study, a listing of deaths will be provided, and all relevant information will be discussed in the patient narrative included in the CSR.

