This Statistical Analysis Plan (SAP) describes the planned analysis and reporting for Teva Branded Pharmaceutical Products R&D, Inc. study TV48125-PN-20028, (A Multicenter, Randomized, Double-Blind, Placebo-Controlled, Proof of Concept Study of the Efficacy and Safety of Fremanezumab for Treatment of Patients with Fibromyalgia), and was written in accordance with SOP GBP_RD_702 (Statistical Analysis Plan).

The reader of this SAP is encouraged to read the study protocol for details on the conduct of this study, the operational aspects of clinical assessments, and the timing for completing the participation of a patient in this study.

The SAP is intended to be in agreement with the protocol, especially with regards to the primary and all secondary endpoints and their respective analyses. However, the SAP may contain more details regarding these particular points of interest, or other types of analyses (e.g. other endpoints). When differences exist in descriptions or explanations provided in the study protocol and this SAP, the SAP prevails; the differences will be explained in the Clinical Study Report (CSR).

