8. SAFETY ANALYSIS

8.1. General

The safety analysis set will be used for all safety analyses. Summaries will be presented by treatment group as actually received unless otherwise stated.

In the Study TV48125-PN-20028 protocol amendment 04, the data collections had been changed:

- Some data are not collected as they were prior to protocol amendment 04 at some visits; for example, clinical laboratory data are no longer collected at visits 4 and 5.
- Follow-up visit was removed

This section reflects data collections in the study including data collected prior to Study TV48125-PN-20028 protocol amendment 04. For by-visit summaries, all data collected in the study will be summarized.

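### SAP 8.10 does not carry forward the protocol's descriptive C-SSRS summary, so a named safety endpoint has no planned by-arm count, denominator or baseline comparison

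*SAP*

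**What the plan says.** Protocol 2.1 and SAP 1.1 both list suicidal ideation and behavior, measured by the C-SSRS, among the safety and tolerability endpoints.

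Protocol 9.8.2 plans the analysis: "Changes in laboratory, ECG, vital signs measurements, and C-SSRS data will be summarized descriptively". A listing comes on top of that: "All values will be compared with predefined criteria to identify potentially clinically significant values or changes, and such values will be listed".

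SAP 8.10 describes how the scale is administered (Baseline/Screening version at Visit 1, Since Last Visit version at every other time point) and notes that significant findings need evaluation by the investigator. Its only planned output is: "Patients having positive findings will be listed".

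On precedence, the SAP Introduction states: "When differences exist in descriptions or explanations provided in the study protocol and this SAP, the SAP prevails". It adds that differences will be explained in the clinical study report. SAP Section 18, which is meant to record changes from the protocol's analyses, reads NA.

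**The concern.** A listing of patients with findings is not a summary of an endpoint. It gives no number or percentage by arm, and no count of patients assessed. SAP 8.10 also leaves three things unstated: what makes a finding positive, whether pre-dose findings belong in the listing, and what a post-dose finding is compared with.

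What is at stake is the safety result for an endpoint that the trial names and measures repeatedly. If the SAP is followed literally, the report need not show how many patients in each arm had ideation or behavior after dosing, or how many of those had something new or worse than before. The departure from the protocol would also be missing from the section of the SAP meant to record it.

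**Working it through.** The documents give no numerical claim on this point to reproduce. The check compares the texts, with one count and one illustration.

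**Step 1: scheduled assessments.** Protocol Table 1 marks the C-SSRS at V1 to V7, which is 7 assessments. Footnote d puts every assessment listed above IMP administration before dosing, and the C-SSRS row stands above that row. V3 is therefore pre-dose. Pre-dose: V1, V2, V3 = 3. Post-dose: 7 − 3 = 4 (V4 to V7).

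**Step 2: the four data types named together in Protocol 9.8.2.**

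| Data | Protocol 9.8.2 | SAP |
|---|---|---|
| Laboratory | descriptive summary | 8.5: values, changes and shifts from baseline |
| Vital signs | descriptive summary | 8.7: values and changes from baseline |
| ECG | descriptive summary | 8.8: values, changes and shifts from baseline |
| C-SSRS | descriptive summary | 8.10: listing only |

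Three of the four keep a summary. The SAP also treats listing and summarizing as separate outputs, since Section 9 plans both for local tolerability.

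**Step 3: can another SAP rule supply the summary?**
- SAP 8.1 says: "Summaries will be presented by treatment group as actually received unless otherwise stated". It also says that by-visit summaries use all data collected, before and after amendment 04. Both statements govern summaries that exist, and 8.10 specifies none.
- SAP 4.2 gives a general baseline (last non-missing value before first dose), but 8.10 plans no comparison that would use it.
- SAP 8.3 tabulates treatment-emergent adverse events. The protocol expressly turns clinically significant examination, vital-sign and ECG findings into adverse events (Protocol 7.5 to 7.7). For a significant C-SSRS finding, Protocol 7.10 requires only evaluation by the investigator.

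**Step 4: can ideation be present before dosing?** The trigger for ideation in exclusion h is "a response of “yes” to questions 4 or 5 on the suicidal ideation portion of the C-SSRS", over the last 12 months. Suicidal behavior, and an assessment of significant risk at the Screening or Randomization Visit, also exclude. A milder ideation item answered yes is not in itself a trigger, and stable, treated major depression is allowed under exclusion j. Milder pre-dose ideation is therefore possible. The documents do not say how common it is.

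**Step 5: the choice of baseline matters.** Under SAP 4.2 the baseline would normally be the V3 assessment, on the Since Last Visit form, which covers only the time since V2 (about two weeks). Ideation reported at V1 but not at V3 would then not count as present at baseline. The highest category over V1 to V3 would count it.

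**Step 6: illustration of what a by-arm count would add.** With 0 affected patients among n, the exact two-sided 95% upper limit is 1 − 0.025^(1/n).
- n = 80 (planned per arm): 1 − 0.025^(1/80) = 4.5%.
- n = 50 (assumed, because the study stopped early and the final number is not given): 1 − 0.025^(1/50) = 7.1%.

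The chance of at least one case in an arm is 1 − (1 − p)^n. For assumed true incidences p of 1%, 2% and 5% it is 55%, 80% and 98% with n = 80, and 39%, 64% and 92% with n = 50. Even a zero count is therefore a reportable result, but it needs the denominator that a listing of positives does not supply.

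**The case against.** The best defense is that the SAP is silent about a summary and does not cancel one. It says that it is intended to agree with the protocol, a listing is compatible with a summary, and Protocol 9.8.2 plans both. This stands as a limit on wording: a reader might infer that the sponsor deliberately replaced the summary, and the documents do not show that. They show an omission. The omission still matters, because the SAP is the document the analysis follows and it specifies no C-SSRS table.

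A reader might also infer that the listing will mix pre-dose and on-treatment ideation beyond separation. No listing layout is given, data are collected visit by visit, and SAP 4.4 numbers study days from the first dose, so arm and timing may well be shown. What can be said is that 8.10 does not require it.

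Adverse event tables do give partial cover. Ideation or behavior recorded as an adverse event would appear by treatment group, including in the serious-event and discontinuation tables, and Protocol 4.3 says that a positive C-SSRS may meet criteria for stopping the IMP. The loss is mainly of findings never recorded as adverse events.

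Exclusions g, i and j (HADS depression subscore above 14; psychotic or bipolar disorder; untreated moderate or severe depression or anxiety disorder) narrow the group with baseline ideation without removing it.

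Finally, Section 18 is not the only route to disclosure. The SAP Introduction points to the clinical study report, and Protocol 9.16 allows an amendment, the SAP or the report. NA is thus an inconsistency in the record, not evidence that the change would stay hidden.

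**Conclusion.** The point holds as a gap between the protocol and the SAP. One named safety endpoint, with four scheduled post-dose assessments per patient, has no planned by-arm result or denominator, and 8.10 does not say how new findings are separated from those present at V1 to V3. Of the four data types that Protocol 9.8.2 says will be summarized, the C-SSRS is the only one left without a summary in the SAP.

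The size in patients cannot be stated, because neither document gives an event rate or the final sample size. The limits and probabilities under working rest on the planned 80 or an assumed 50 per arm and on assumed incidences, and are context only. The conclusion assumes that the SAP is followed as written and that no table shell outside these documents supplies the summary.

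This is a descriptive output in a proof-of-concept study already stopped for futility, and no efficacy inference depends on it. It should still be corrected, because the endpoint is a named safety measure and the data are already collected. The point concerns reporting only and implies no clinical rule.

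**What to change.** In SAP 8.10:

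1. Define a positive finding.
2. Add one descriptive table on the safety analysis set, by treatment actually received. Show the number assessed, n (%) with any suicidal ideation after the first dose, n (%) with any suicidal behavior after the first dose, and n (%) new or worsened relative to a stated pre-dose baseline.
3. State that baseline: either the SAP 4.2 definition, or the highest pre-dose category over V1 to V3 written in as an express exception to 4.2.
4. Keep the listing, showing treatment arm and visit or a pre-dose/post-dose flag.

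If the summary is dropped on purpose, replace NA in Section 18 with that change and the reason.

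The cost is one table and a few lines of SAP text. No new data are needed, and SAP 2.5.2 provides for amendments approved before database lock.
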